4.1 Dispositions of Subjects and Analysis Set

Summaries based on all screened patients will include disposition of patients (eligibility), analysis set inclusion (yes/no), patient status (completed or discontinued), and the main reason for study discontinuation. Summaries based on the SAF will include number of patients per center and number of patients per visit. These results will also be provided in listings.

Violated inclusion and exclusion criteria (eligibility) will be noted in a listing.

Statistical Analysis Plan	Final Analysis
CLN-PRO-004	12/23

A patient has completed the study when the end of study CRF indicates that the patient "Study completed". A discontinuation of screen failure is defined as the patient was screened but did not pass the study procedure criteria.

Please note, a patient is assessed for inclusion and exclusion criteria at the preoperative screening visit. On day of the surgery (Day 1), eligibility is re-assessed against the inclusion/exclusion criteria. If the patient does not pass eligibility, then the site will update the inclusion/exclusion violation. The patient will become a screen failure.

The date of visit (if available; yes/no) will be used to indicate if a patient was expected for the visit, whether the respective visit was conducted

4.2 **Protocol Deviations**

All major protocol deviations will be documented throughout the study and will be provided in a listing.

4.3 Demographics and Other Baseline Variables

Demographic and other baseline variables will be descriptively analyzed for the SAF.

Demographic data

Demographic data (age, gender, ethnicity, race, body height [cm], body weight [kg], body mass index [BMI; kg/m²]) will be summarized and listed. Demographic data will be summarized and listed for screen failure patients as well.

Medical History

Medical history will be coded by Medical dictionary for regulatory activities (MedDRA). Patients with significant previous or existing concomitant diseases (medical history) will be listed.

PAD surgical/interventional history will be listed.

Smoking History

Count and percentage of current / past / never smokers will be tabled. Pack years (combined current and past smokers) will be summarized. Smoking history data will also be listed.

• Pack years will be calculated for current smokers and former smokers. Pack years will be interpreted as the number of cigarette packs used over the course of their smoking history.

Pack years were calculated as: Number of Packs per Day * 365.25 * smoking years

Notes: For patients reporting "< $\frac{1}{2}$ pack", $\frac{1}{2}$ was used in the calculation.

Pre-study Angiography/CT Angio and Vein Mapping

Angiography data will be tabulated and listed.

ECG at Screening

Statistical Analysis Plan	Final Analysis
CLN-PRO-004	13/23

Result of 12-lead ECG at screening will be presented with frequency tabulations.

Documentation of Surgery and Any Complications

Implantation of HAV and documentation of surgical procedure, any complications (e.g., prolonged oozing at anastomoses), and interventions will be listed.

Pregnancy Test

Pregnancy test results will be summarized and listed.

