1.5 Sample Size Estimation

Up to 25 patients were planned, and 15 patients were recruited into the study. As this Phase 2 study is one of the first studies of the HAV in humans with PAD, the number of patients was chosen in order to provide preliminary evidence of safety and efficacy of the HAV to allow the initiation of further trials in larger numbers of patients.

The study is not powered to assess the efficacy of the HAV.

2 Efficacy and Safety Variables

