3.4 Interim Analysis

Data Monitoring Committee (DMC) reports will be provided during the course of the study.

Statistical Analysis Plan	Final Analysis
CLN-PRO-004	11/23

Endpoints will be assessed over a period of up to 60 months after HAV implantation.

- The **primary analysis** of the study will be based conducted on the earlier of a) when the final patient enrolled reaches 12 months post-implant or b) all subjects enrolled in the initial 36 month accrual period have reached 12 months post-implant. The SAP will call this the 1-year analysis.
- The **final analysis** will occur at the end of the study, when all patients have completed or exited the study.

The database extraction for the **1-year analysis** will include all study data collected at the time of the database extraction. The by-visit tables and figures will display all time points present in the data, including visits after the Month 12 visit (where applicable). Event tables (such as concomitant medications, AEs), will include all events during the study. Listings will display all study data available, including data collected after the Month 12 visit.

The database for the final analysis will include all study data and by-visit tables will display all study timepoints.

4 Statistical Evaluation

All tables, figures and listings will be produced using SAS (v9.4 or a more recent version).

Unless otherwise stated, categorical data will be presented using counts and percentages, whilst continuous parameters will be summarized using standard summary statistics as appropriate (n, mean, standard deviation [SD], median, minimum, maximum, 25th percentile, and 75th percentile). Minima and maxima will be quoted to the number of decimal places as recorded in the case report form (CRF); means, SDs and medians will be quoted to one further decimal place.

The closest non-missing values prior to implantation on Day 1 will be used as baseline values.

Unless otherwise stated, all confidence intervals will be presented as 95% two-sided intervals. For categorical endpoints, if all values are either success or failure, the exact CI will be presented.

As no sample size assessment has been undertaken, all analysis results are considered to be exploratory.

Details on the specification, definition, calculation and analysis of the efficacy and safety endpoint variables are given in Section 2 and the following sections.

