4.3 Demographics and Other Baseline Variables

Demographic and other baseline variables will be descriptively analyzed.

Demographic data

Demographic data (age, gender, ethnicity, race, body height, body weight, BMI) will be summarized and listed.

Medical History

Patients with significant previous or existing concomitant diseases (medical history) will be listed.

Smoking History

08 September 2016

SAP (version 1.0)

Confidential

Statistical Analysis Plan	Final Analysis
CLN-PRO-004	11/19

Count and percentage of current / past / never smokers will be tabled. Pack years (combined current and past smokers) will be summarized. Smoking history data will also be listed.

Pre-study Angiography/CT Angio and Vein Mapping

Angiography data will be tabulated and listed.

Eligibility (inclusion/exclusion criteria)

Eligibility data will be listed.

ECG at Screening

Result of 12-lead ECG at screening will be presented with frequency tabulations.

Documentation of Surgery and Any Complications

Implantation of HAV and documentation of surgical procedure, any complications (e.g., prolonged oozing at anastomoses), and interventions will be listed.

Pregnancy Test

Pregnancy test result will be summarized and listed.

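### SAP 4.3 reports lifetime cigarette packs under the name pack years, so each smoker's value is 365.25 times what the label denotes

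*SAP*

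**What the plan says.** SAP version 2.0, section 4.3, Smoking History, makes four statements about this variable.

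- How it is reported: "Pack years (combined current and past smokers) will be summarized".
- Who gets a value: "Pack years will be calculated for current smokers and former smokers". Never smokers get none.
- What it means: "Pack years will be interpreted as the number of cigarette packs used over the course of their smoking history".
- How it is derived: "Pack years were calculated as: Number of Packs per Day * 365.25 * smoking years".

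Section 4.3 treats it as description only: "Demographic and other baseline variables will be descriptively analyzed for the SAF". Under the general rules in SAP section 4, "continuous parameters will be summarized using standard summary statistics as appropriate", which the SAP lists as n, mean, SD, median, minimum, maximum and the two quartiles.

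SAP version 1.0 used the same name and gave no formula, so the 365.25 factor appears only in the current version. The protocol collects smoking history (sections 7.1 and 7.5.1) and does not define pack-years.

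**The concern.** The name of the variable is a familiar unit of smoking exposure, and the rule produces a different quantity. A reader of the baseline table would see values in the thousands or tens of thousands under a unit normally read in tens.

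The study has one arm, and protocol section 2.5.3 plans to set its data against historical data on synthetic bypass grafts. Readers making that comparison will look at the baseline table to judge whether the populations are alike. A smoking-exposure row that cannot be taken at face value is a hindrance there, although a small one.

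**Working it through.** **Inputs**

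- Formula: SAP 4.3, packs per day × 365.25 × smoking years.
- Conventional pack-years: packs per day × smoking years. The documents do not define this; it is assumed here as the ordinary meaning of the unit.
- Patients: SAP 1.5 states "Up to 25 patients were planned, and 15 patients were recruited into the study", so at most 15 are affected, less any never smokers.
- Smoking histories: the documents give none, so those below are illustrative assumptions, not trial data.

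The documents print no pack-year result, so there is no figure of the plan's own to reproduce.

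**Step 1: units.** (packs/day) × (365.25 days/year) × (years) = packs. The days and the years both cancel.

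**Step 2: ratio.** (packs/day × 365.25 × years) ÷ (packs/day × years) = 365.25, whatever the inputs, provided exposure is not zero.

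**Step 3: individual values.**

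| Packs/day | Years | SAP formula | Packs/day × years |
|---|---|---|---|
| 0.5 | 30 | 0.5 × 365.25 × 30 = 5,478.75 | 15 |
| 1 | 40 | 1 × 365.25 × 40 = 14,610 | 40 |
| 1.5 | 45 | 1.5 × 365.25 × 45 = 24,654.375 | 67.5 |

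Read literally as pack-years, 14,610 over 40 years implies 14,610 ÷ 40 = 365.25 packs a day.

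**Step 4: summary statistics.** A constant multiplier carries through to location and spread alike. For the three values above:

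- Mean: (15 + 40 + 67.5) ÷ 3 = 40.83; × 365.25 = 14,914.4.
- SD: 26.26; × 365.25 = 9,591.4.
- Median: 40; × 365.25 = 14,610.

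Quartiles, minimum and maximum scale in the same way. Only n is unchanged.

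The SAP's separate convention of using one half for patients who report less than half a pack does not alter the ratio.

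**The case against.** The strongest reply is that nothing is miscalculated. The SAP says what it means by the variable, a count of packs, and its formula computes that. On this view the defect is a matter of naming, and the benchmark it fails is a convention found nowhere in the documents.

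Much of this stands. Definition and formula do agree, and the conventional meaning is an assumption, though hardly a contested one. But internal agreement does not repair the label. The SAP names the reported quantity pack years and does not say that its special definition will be printed with the output.

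Two limits also stand. First, the body of SAP version 2.0 section 9 (Miscellaneous) and any table shells are not in the text available for review, so one can say only that no visible text corrects the label. The values above are what the SAP implies, not output that has been seen.

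Second, the consequence is small. The study tests no hypothesis, its results are declared exploratory, and no endpoint, eligibility rule or specified model uses the variable. The optional subgroup analyses in SAP 3.2 name no smoking variable, and a constant factor would leave the ordering of patients unchanged. A mean in the thousands would also strike most readers as implausible.

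**Conclusion.** The point holds and is minor. As written, the SAP reports lifetime packs as pack years, overstating the labelled quantity by exactly 365.25 for every smoker and in every summary statistic except n. This rests on the ordinary meaning of a pack-year and on the SAP being followed literally. No efficacy or safety conclusion depends on it. No information is lost either, since dividing by 365.25 recovers the conventional value.

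**What to change.** Choose one of two changes.

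1. Report pack-years: define the variable as packs per day × smoking years, and delete both the 365.25 factor and the sentence that interprets the variable as packs. Removing the factor alone would leave the definition contradicting the formula.
2. Report lifetime packs: keep the formula and rename the variable total packs smoked in the SAP, the table and the listing.

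Option 1 gives a figure that can be read directly beside other series. The half-pack convention can stay as a footnote under either option.

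The SAP puts the derivation in the past tense, so check whether the smoking-history table and listing already exist. The cost is one or two lines of SAP text, one line of code or a label change, and a rerun of those two outputs if they have been produced.

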4.4 Efficacy Analysis

4.4.1 Analysis of Primary Efficacy Parameters

Efficacy Objective 1:

Primary, primary assisted, and secondary patency rates of the HAV at Month 12 with evaluation of patency will be described.

Primary patency is defined as the functional patency until any type of intervention.

Primary assisted patency is defined as an HAV still working without thrombosis.

Secondary patency is defined as the functional patency, with or without preceding successful interventional or surgical procedures to maintain or reestablish patency, until either final failure or the HAV is abandoned.

All patients start out in primary patency. A patient is not expected to flow from primary, to assisted, to secondary patency directly. For example, an abandonment can occur after the HAV implant, that ends the primary patency and the patient never went into an assisted or secondary status.

Primary patency	 Start: HAV implantation date End: earliest start date from assisted, secondary, or abandonment status
Primary assisted patency	 Start: any type of intervention to HAV End: earliest start date from secondary or abandonment status
Secondary patency	Start: earliest thrombosis AE start date;End: abandonment date

Many parts are used to derive patency:

Abandonment	 Source: AE eCRF Terms: "Anastomotic stenosis", "Arterial bypass stenosis" ,"Arterial bypass thrombosis", and "Arterial bypass occlusion" And action taken is recorded as "Patient withdrawn from study", or "None"
-------------	--

Final Analysis 14/23

Stenosis	 Source: AE eCRF Terms of "Anastomotic stenosis" "Arterial bypass stenosis"
Thrombosis	 Source: AE eCRF Terms of "Arterial bypass thrombosis" "Arterial bypass occlusion"
Interventions for stenosis	 Source: Interventions eCRF Intervention to treat stenosis: Intervention type on eCRF as "Intervention to treat anastomotic or mid-HAV stenosis but without HAV thrombosis.
Interventions for thrombosis	 Source: Interventions eCRF Intervention to treat thrombosis: Intervention type on eCRF as "Intervention to treat anastomotic or mid-HAV stenosis and with HAV thrombosis.
End of study	Source: End of study eCRF

Data handling for this rate will be as followed

The assignment to a patency (yes/no) (primary, primary assisted, secondary patency) will be verified during the Data Review Meeting (DRM) using all data of CRF sections referring to HAV patency, clinical examination of the HAV site, doppler ultrasound assessment of HAV patency, HAV intervention, premature discontinuation, and AEs.

Patency rates will be presented with frequency tabulations showing patient numbers and patency rates for Month 12.

Clopper-Pearson confidence intervals (CI) will be presented for frequency counts of patency rates.

Kaplan-Meier (K-M) curves for primary, primary assisted, and secondary patency will be created at the 1-year report and for all subsequent reports. K-M curves will be provided using two censoring methods:

- a. Patients who die, withdraw from the study, or are lost to follow-up are censored at the day of the respective event.
- b. Patients who die, withdraw from the study, or are lost to follow-up are considered as having suffered failure of secondary patency at the day of the respective event.

Efficacy Objective #2:

Hemodynamically significant stenosis (>70% by duplex ultrasound criteria): The duplex ultrasound parameters will be summarized by planned visit up to Month 12.

- Frequency of stenosis occurrence, location of stenosis, and presence of aneurysm.
- Numeric summary of volumetric flow rate and inner diameter of HAV mid bypass.

A stenosis event can occur between planned study visits (i.e. Unscheduled Visits). A "by visit"

Statistical Analysis Plan	
CLN-PRO-004	

summary will represent the stenosis event/information that occurred before or on the planned visit. For example, the summary at Day 5 will denote the number of patients who had stenosis occur up to Day 5 or on the Day 5 visit. Similarly, the Day 29 summary will denote the number of patients with stenosis events that occurred after Day 5, and up to Day 29 (inclusive of Day 29).

The time of first stenosis (in days) will be summarized and calculated as number of days from HAV implantation to date of first stenosis event: Date of Stenosis – Date of Day 1 + 1. Patients who did not have a stenosis event will not contribute a value for this summary.

Please note, the clinical duplex will be recorded for all visits. Results after Month 12 **will not** be summarized in tables and will be provided in the listings.

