# 9.3. Efficacy Analyses

Primary, primary assisted, and secondary patency rates of the HAV at Month 12 and at all other post-surgery visits with evaluation of patency will be described.

Confidential

Primary patency is defined as the functional patency until any type of intervention; primary assisted patency is defined as an HAV still working without thrombosis; secondary patency is defined as the functional patency, with or without preceding successful interventional or surgical procedures to maintain or reestablish patency, until either final failure or the access is abandoned. Early discontinued patients prior to the visit of interest will be determined as being non-patent irrespective of the reason for discontinuation.

The rate and type of interventions needed to maintain / restore patency in the HAV will be descriptively tabulated.

The absolute change from baseline (Day 1) values to all post-surgery visits of duplex ultrasound parameters will be summarized. Summary statistics will also be provided at each time point.

The methods and endpoints regarding the efficacy parameters employed in this study are consistent with current clinical practice and are meaningful to the research community. Every attempt has been made to minimize the variability on the part of the surgeon when using this product. The results of this study will be used to determine the sample size of subsequent clinical studies.

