4.4.4 Other Efficacy Variables

High Resolution Ultrasound

Doppler ultrasound (HAV patency) high resolution ultrasound data will be listed.

Time to loss of patency

Time after first implantation of HAV until loss of patency (primary, primary assisted and secondary) will be separately presented in tables using descriptive statistics. The time to loss of patency will be verified during the DRM using all data from the CRF including the information used for patency rates at each visit and information on any AEs and consequent interventions.

Patients discontinued early with the HAV still patent, will be censored at that timepoint.

The median times (or the lower quartile – in case the median is unable to be estimated) will be presented together with the respective 95% CIs using Kaplan-Meier estimates. In case of small numbers of events these analyses may be skipped.

For the 1-year interim analysis, time to loss of patency will be reviewed for the first 12 months, and rates of 3, 6, and 12 months will be presented. For the final analysis, time to loss of patency will be reviewed for the entire study and rates of 3, 6, 12, 24, 36, 48, and 60 months will be presented.

Focused vascular assessment exam will be listed.

Angiography and Endothelium-dependent, flow-mediated vasodilation data will be listed.

5 Safety Analysis

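### SAP 4.4.1 defines assisted and secondary patency as cumulative from implantation but tabulates them as successive statuses, and nothing says which rule governs the Month 12 rates

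*SAP*

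**What the plan says.** SAP 4.4.1 first defines the three endpoints in words:

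- Primary: "Primary patency is defined as the functional patency until any type of intervention".
- Primary assisted: "Primary assisted patency is defined as an HAV still working without thrombosis".
- Secondary: "Secondary patency is defined as the functional patency, with or without preceding successful interventional or surgical procedures to maintain or reestablish patency", ending at final failure or abandonment.

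Protocol 9.3 gives the same definitions; its secondary wording is "secondary patency is defined as the functional patency, with or without preceding successful interventional or surgical procedures to maintain or reestablish patency".

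A Start/End table follows in the same SAP section:

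- Primary starts at implantation. "End: earliest start date from assisted, secondary, or abandonment status".
- Primary assisted: "Start: any type of intervention to HAV". It ends when secondary or abandonment status begins.
- Secondary: "Start: earliest thrombosis AE start date;End: abandonment date".

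The SAP's example of a graft abandoned straight from primary patency says that such a patient never held the other two statuses.

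SAP 4.4.4 uses a single time origin for all three: "Time after first implantation of HAV until loss of patency (primary, primary assisted and secondary) will be separately presented".

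**The concern.** By the written definitions, an HAV that is open and has had neither an intervention nor a thrombosis has primary, assisted and secondary patency at once. In the table the statuses follow one another without overlap, and an HAV enters assisted or secondary status only after something has happened to it. An event-free HAV never gets a start date for either.

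All three rates are primary efficacy endpoints (Protocol 4.2.1, SAP 2.3), with Month 12 as the primary time point. Protocol 2.5.3 intends to set the data against historical synthetic grafts, and Protocol 9.3 intends to use the results to size later studies. A secondary rate that covered only HAVs that had thrombosed could fall below the primary rate, which the definitions do not allow. It could not be compared with cumulative rates from elsewhere.

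**Working it through.** The plan states no expected patency rate and no power calculation, so there is no figure to reproduce. The check is one of logic, followed by an illustration.

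**Step 1. Expand the table.** Let 0 be implantation, A the first HAV intervention, T the first thrombosis AE and B abandonment. Replace each reference to another row's start by its event.

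| Row | Table: start | Table: end | Definitions: start | Definitions: end |
|---|---|---|---|---|
| Primary | 0 | min(A, T, B) | 0 | min(A, T, B) |
| Assisted | A | min(T, B) | 0 | min(T, B) |
| Secondary | T | B | 0 | B (or final failure) |

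The End events agree, apart from final failure, which the table omits. The conflict lies in the two Start cells.

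**Step 2. Apply both rules to single patients.**

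- Event-free HAV (no A, T or B): the definitions give all three patencies; the table gives primary only.
- First event a thrombosis, treated one day later (A = T + 1): the table's assisted period starts at T + 1 and ends at T, a length of −1 day. The secondary period starts on the day of occlusion.

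**Step 3. Illustrate the size.** SAP 1.5 gives 15 recruited patients. The split at Month 12 is an assumption, not trial data: 9 event-free, 1 patent after intervention without thrombosis, 3 patent after treated thrombosis, 2 abandoned. Intervals are Clopper-Pearson 95%, as SAP 4.4.1 specifies: lower limit = 2.5% quantile of Beta(x, n − x + 1), upper limit = 97.5% quantile of Beta(x + 1, n − x).

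| Month 12 rate | Definitions | Table read literally |
|---|---|---|
| Primary | 9/15 = 60.0% (32.3 to 83.7) | 9/15 = 60.0% (32.3 to 83.7) |
| Assisted | (9 + 1)/15 = 66.7% (38.4 to 88.2) | 1/15 = 6.7% (0.2 to 31.9) |
| Secondary | (9 + 1 + 3)/15 = 86.7% (59.5 to 98.3) | 3/15 = 20.0% (4.3 to 48.1) |

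**Step 4. Vary the split.** Adding splits of 12/1/1/1, 9/0/4/2 and 6/3/4/2 in the same order:

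- Secondary: 86.7% to 93.3% by the definitions, 6.7% to 26.7% by the table.
- Assisted: 60.0% to 86.7% by the definitions, 0% to 20.0% by the table.
- If all 15 are event-free, the definitions give 15/15 (78.2 to 100) for both rates and the table gives 0/15 (0 to 21.8).

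**Step 5. Check comparability.** Rates from mutually exclusive statuses cannot sum above 100%. The Month 12 estimates from the earlier PAD study (Protocol 2.4.3) sum to 63.3 + 63.2 + 84.2 = 210.7%, so they are of the cumulative kind. Rates built from the table's statuses could not be set beside them.

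**The case against.** The strongest reply is that the table is only a status timeline whose End dates supply the loss dates. Step 1 supports this: the expanded End events are essentially the right ones. Combined with the implantation origin in SAP 4.4.4, they give the cumulative result. The second Kaplan-Meier censoring method in SAP 4.4.1 points the same way. It treats any patient who dies, withdraws or is lost as failing secondary patency, which presumes that every patient had it to lose. The Data Review Meeting (SAP 4.4.1 and 8) also verifies each yes/no assignment against examination, ultrasound, intervention, discontinuation and AE data before sign-off.

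All of that stands, and it rules out some stronger readings:

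- A reader might infer that the SAP will count event-free HAVs as not patent, or will draw Kaplan-Meier curves with different patients and time zeros. Neither is stated, and SAP 4.4.4 contradicts the second.
- The negative assisted period in Step 2 shows that the table does not work as a derivation. It is not a reported error, because the SAP plans no output for time spent in assisted status.
- A reader might size the effect by applying the earlier PAD study's rates to 15 patients. Those are Kaplan-Meier estimates with deaths censored, not simple proportions, and primary (63.3%) slightly exceeds assisted (63.2%). That study also required two patent below-knee vessels, against one here.

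The stakes are also limited: there is no hypothesis test and the SAP calls all results exploratory.

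The reply does not settle which rule produces the Month 12 proportions. SAP 4.4.4 governs time to loss, and the censoring method governs the curves. The SAP never says to disregard the Start cells, and the review meeting is given no rule for choosing between the two versions. In an open-label trial, where the sponsor signs the patency decisions after patient listings are supplied, that rule should be fixed beforehand.

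**Conclusion.** The point holds as an internal inconsistency in SAP 4.4.1 that leaves the derivation of a primary endpoint open. The definitions and the table cannot both be followed for any HAV that is open and event-free. Other parts of the SAP favour the cumulative reading, but nothing makes it govern the Month 12 rates. It does not follow that the reported rates are or will be wrong.

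The illustrative gap (assisted 66.7% against 6.7%, secondary 86.7% against 20.0%) is the worst case, in which the table is applied literally and the review meeting corrects nothing. Its size rests on the assumed split. Its direction does not: whenever any HAV is open and event-free at Month 12, the literal table understates both rates. The primary rate is unaffected. The change should be made before the rates are derived.

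**What to change.** In the SAP 4.4.1 table, set Start to the HAV implantation date in all three rows and write each End as events:

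- Primary: earliest of first HAV intervention, thrombosis, or final failure/abandonment.
- Primary assisted: earliest of thrombosis or final failure/abandonment.
- Secondary: final failure/abandonment.

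The End cells must be rewritten together with the Start cells. The primary and assisted End cells currently point to other rows' Start dates, so moving only the two Starts to implantation would end primary and assisted patency on the day of surgery.

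Add two sentences: every implanted patient is in the denominator of each rate, and an event-free patent HAV counts as patent in all three senses. Add a programming check that, for each patient, primary duration ≤ assisted duration ≤ secondary duration.

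The cost is rewording about four cells (two Starts and two Ends, plus final failure added to the secondary End) and one check. No new data are needed.
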